6. STUDY PROCEDURES

Data Collection

A clinical research coordinator blind to group assignment will administer standardized telephone interviews, scheduled at the participants' convenience. On the rare occasion that a woman is unable to complete the surveys by telephone, the coordinator will send a link to a secure electronic Redcap survey or mail a hard copy of the surveys with a postage paid envelope in order to do everything we can to minimize missing data. Data is directly entered into the Redcap software system. Redcap is programmed with quality controls that facilitate rigorous data collection, such as not allowing interviewers to skip questions.

Data Collection Schedule

Measures and Data Collection Schedule

Aim	Construct	Instrument	# of Items	T1 Week 0	T2 Week 8	T3 Week 20	T4 Week 44
	Characteristics	Demographics and Clinical Characteristics	9	X			
Aim 1	Participation & Productivity	PROMIS® (Satisfaction and Ability to Participate in Social Roles and Activities) Disability Days and WLQ-SF Individual activity targets	16 25+2 3-9	X	X	X	X
Aim 2	Quality of Life	FACT-G	28	X	X	X	X
Exploratory Aim	Adaptive Coping	Brief COPE subscales	6	X	X	X	X
Exploratory Aim	Goal Adjustment	GDGRS	10	X	X	X	X
Exploratory Aim	Distress	Hospital Anxiety and Depression Scale (HADS)	14	X	X	X	X
	Perceived benefit	Perceived Benefit Questions	5		X		

The coordinators will administer the outcome assessment battery by telephone upon enrollment (T1), after completion of the most intensive portion of the intervention (T2), after completion of the full intervention (T3) and six months after completion of the intervention (T4). Coordinators begin to call participants up to three weeks before the survey target date to schedule the survey; they will continue to call participants until either the survey is completed or four weeks passes beyond the target date. If participants are unable or unwilling to complete the outcome assessments by telephone, we will offer them the opportunity to complete the measures on paper (mailed with a hard copy and postage paid return envelope) or electronically (a link to a Redcap survey will be sent by email).

Measures

Eligibility Assessment

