Individual Activity Targets (secondary outcome): During the first session of the intervention and control conditions, the occupational therapist elicits the participant's individual recovery goals. The participant rates each activity with Likert scales for three characteristics: frequency of current performance (very often, often, once in a while, almost never, never), importance of the activity (1-10), and satisfaction with the activity (1-10). These ratings were used in a similar study by our team and provided a simple and pragmatic tool for assessing individualized outcomes.[62]

Quality of Life

Quality of Life: The *Functional Assessment of Cancer Therapy- (FACT-G)* is a 28-item self-report measure of health-related quality of life specifically designed for breast cancer patients.[40, 41] The items of the tool assess perceived well-being in physical, social, emotional, and functional domains. Subscale scores are derived in each domain as well as a total score. [41]

Exploratory Outcomes

Coping: *Brief COPE*.[42] Our pilot research has suggested that BA/PS increases participants' use of active coping, planning and positive reframing.[29] These coping styles are measured by three subscales of the Brief COPE. The Brief COPE has been shown to have excellent psychometric properties among cancer patients including evidence of construct, convergent and concurrent criterion validity.[63] To minimize respondent burden, we will not administer the 28-item Brief COPE, but will instead utilize the three subscales of interest.

Goal adjustment: *Goal Disengagement and Goal Reengagement Scale (GDGRS)*.[43] The GDGRS is a 10-item scale that measures two aspects of goal adjustment. Four items measure dispositional goal disengagement (i.e. the general inclination to relinquish untenable goals). Six items measure dispositional goal reengagement (i.e., commit to new goals). The internal consistency of the scales is generally high.[64] We will use the GDGRS to explore the potential efficacy of BA/PS on goal adjustment.

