Non-prescriptive. The BA/PS interventionist does not directly give advice or prescriptions. Behavioral Activation and Problem-solving Treatment were developed to treat depression and one active ingredient of those therapies is to teach patients to actively identify their own solutions to problems in living. We have found this technique is also beneficial when addressing participation because the cancer survivor is the expert in his or her lifestyle, routines, and environment. A participant in a pilot study of Behavioral Activation that we are conducting at Johns Hopkins (K23HL138206; PI: [name]) noted this emphasis was refreshing and in stark contrast to his post-hospitalization experiences of rehabilitation (i.e., “they mostly told me what I should do.”).

[figure not shown]
Session 1. The interventionist presents the rationale for BA/PS, promotes a positive problem orientation, and educates about the framework for problem-solving and action planning. The interventionist then administers the Canadian Occupational Performance Measure[76] to elicit participant priorities, motivation, and long-term goals. The interventionist then guides the participant in using the BA/PS framework to set a goal, brainstorm solutions to challenges, and create a detailed action plan for the coming week.

Subsequent sessions (once a week for five more weeks, then once a month for three months). The interventionist begins by reviewing the rationale for BA/PS and the previous action plan and elicits information about goal attainment and satisfaction with effort and outcome. If the goal for that week was met, then the interventionist guides the participant to identify another short-term goal for the coming week that would continue the progress towards the long-term goal. If the goal was not met, then the interventionist troubleshoots with the participant to determine whether the challenge was not fully described, whether the goal was too hard, whether the chosen solution or action plan was not effective, or whether more practice is needed. The framework is then used to create a goal and action plan for the coming week.

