Modeling. A longitudinal model fitted with linear mixed methods will be used for each outcome. Numerical outcomes with markedly non-normal distributions, if any, will be modeled with more appropriate error distributions than the default normal (e.g., lognormal or generalized beta distributions). The focus of inference will be the between-group difference in outcome trajectories over the study time points, modeled by a time by group interaction. A random effect for subject will be fitted to account for covariance among repeated measures on the same individuals. If necessary, we will conduct covariate adjustment for baseline factors unbalanced between the groups or predictive of dropout. Time will be modeled as a categorical variable, to avoid the strong assumption of linear trajectories, and therefore the single test for the interaction effect will be a multiple-degree of freedom test. Model-predicted outcome means (a.k.a. LS-Means) by group at each time point will be computed to facilitate interpretation. The overall treatment effect will be computed as the between-group difference in change from baseline (change from T1 averaged over T2 to T4) estimated with a linear contrast.

Handling of Missing Data

Mixed modeling techniques and covariate adjustment will reduce the impact of missing data, as the missingness is not assumed completely at random (MCAR) but conditionally (on the covariates) at random (i.e., MAR, a milder assumption).[82] Should dropout exceed the 20% allowed by the sample size (section C.7.5), non-parametric multiple imputation[83] will be employed to determine the robustness of the conclusions for the main analyses under the milder MAR assumption. Because missing data due to non-ignorable or non-random drop out (i.e., MNAR) does not depend on the observed data, it presents the most complex situation to handle. Because of the non-invasive, supportive nature of the BA/PS intervention, as well as the attention control condition, *a priori*, we do not expect to encounter non-random dropout (and therefore MNAR). However, we will examine the tracking system records and logs with regard to dropout, to determine the main reasons for dropout. If sufficient indication of an MNAR mechanism is found, sensitivity analyses under different assumptions for the missing data mechanism will be conducted, following the methodology described by Molenberghs and Kenward[84] in which the missing data mechanism needs to be modeled explicitly.

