Intent to treat. Our main analyses will utilize an intention-to-treat approach. As the BA/PS intervention is not part of standard practice, cross-over events are not expected to occur. All available data from all participants who undergo randomization will be included in the analyses according to the group assigned, regardless of any post-randomization protocol deviations.

10. Monitoring and Quality Assurance

Safety and Adverse Events

Definitions

Unanticipated Problems Involving Risk to Subjects or Others

Any incident, experience, or outcome that meets all of the following criteria:

- Unexpected in nature, severity, or frequency (i.e. not described in study-related documents such as the IRB-approved protocol or consent form, the investigators brochure, etc)
- Related or possibly related to participation in the research (i.e. possibly related means there is a reasonable possibility that the incident experience, or outcome may have been caused by the procedures involved in the research)
- Suggests that the research places subjects or others at greater risk of harm (including physical, psychological, economic, or social harm).

Adverse Event

An **adverse event** (AE) is any symptom, sign, illness or experience that develops or worsens in severity during the course of the study. Intercurrent illnesses or injuries should be regarded as adverse events.

Abnormal results of diagnostic procedures are considered to be adverse events if the abnormality:

- results in study withdrawal
- is associated with a serious adverse event
- is associated with clinical signs or symptoms
- leads to additional treatment or to further diagnostic tests
- is considered by the investigator to be of clinical significance

Serious Adverse Event

Adverse events are classified as serious or non-serious. A **serious adverse event** is any AE that is:

- fatal
- life-threatening
- requires or prolongs hospital stay
- results in persistent or significant disability or incapacity
- a congenital anomaly or birth defect

- an important medical event

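### The protocol conflicts on when the secondary Individual Activity Targets are first recorded; if in session 1, as their description says, their change-from-T1 baseline is post-randomisation

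*Combined protocol and SAP*

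**What the plan says.** Four parts of the combined protocol and SAP bear on this.

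- **Schedule (section 6, Measures and Data Collection Schedule).** The Aim 1 row, which includes "Disability Days and WLQ-SF Individual activity targets", is marked at T1 (week 0), T2, T3 and T4. The text below the table has the coordinators giving the battery by telephone at enrolment. They are the staff kept blind to allocation.
- **Measure description (section 6, Individual Activity Targets, labelled a secondary outcome).** "During the first session of the intervention and control conditions, the occupational therapist elicits" each woman's own goals for recovery. It continues: "The participant rates each activity with Likert scales for three characteristics", namely frequency, importance and satisfaction.
- **Randomisation and session content (section 6).** Under Process and blinding, the local interventionist tells the participant her assignment and then begins treatment. In BA/PS session 1 the interventionist presents the rationale, "promotes a positive problem orientation" and teaches the framework, and only then conducts the interview that draws out priorities and long-term goals. The paragraph on perceived benefit says that goal setting is not one of the control condition's active ingredients.
- **Analysis (section 9).** The Objective paragraph applies the methods to every outcome. The Modeling paragraph defines the overall effect as the between-group difference in change from baseline ("change from T1 averaged over T2 to T4").

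**The concern.** A target that first exists in session 1 cannot have been rated before it. If the measure description is what happened, the value standing in for T1 was obtained after allocation, in an unblinded session, and in the BA/PS arm possibly after treatment content had been delivered. Three things could then differ by arm because of treatment: which activities are named, how many are named, and how they are rated at the start.

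A change-from-baseline contrast is protected by randomisation only if the baseline cannot respond to allocation. Here it can. The contrast would estimate the follow-up effect minus whatever the first session did to the starting rating, and the data could not separate the two. What is at stake is the interpretation of one secondary outcome.

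**Working it through.** **Figures in the plan.** No SD, correlation, sample size or power is stated for the activity targets, so there is no figure to reproduce for this outcome. The sample sizes that section 9 does state reproduce from n per arm = 2(z₁₋α/₂ + z₀.₈₀)² σ² [(1+2ρ)/3] / δ², with α = 0.05/3 two-sided and three post-baseline visits:

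- PROMIS satisfaction, δ = 3.94, σ = 10: 63 (ρ = 0.2) and 117 (ρ = 0.8), as stated.
- FACT-B, δ = 11.2, σ = 24: 45 and 84, or 83 with α rounded to 0.017; stated 45 and 83.

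The point below does not affect these.

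**How the baseline enters.** Let τ be the true arm difference in the T2-T4 mean and d the arm difference (BA/PS minus control) in the session-1 rating. The change contrast has expectation τ − d, so d passes through one for one with its sign reversed.

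**Size, for illustration only.** Inputs: 120 per arm (section 9: 240 completers of 300, allocated 1:1). Assumed: equal correlation ρ between visits, SD 2.5 on the 1-10 rating, nominal two-sided 5%, and no true effect at follow-up.

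- The variance factor is (1+2ρ)/3 + 1 − 2ρ = (4/3)(1−ρ).
- At ρ = 0.5, SE = √(2 × 2.5² × (4/3) × 0.5 / 120) = √0.0694 = 0.264.
- d = 0.25 (0.1 SD): d/SE = 0.95, and P(|Z + 0.95| > 1.96) = 0.16.
- d = 0.5 (0.2 SD): d/SE = 1.90, giving 0.48.

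The same calculation in SD units, over the range of ρ used in section 9:

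| Baseline shift | ρ = 0.2 | ρ = 0.5 | ρ = 0.8 |
|---|---|---|---|
| 0 | 5% | 5% | 5% |
| 0.1 SD | 12% | 16% | 32% |
| 0.2 SD | 32% | 48% | 85% |

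**The opposite harm.** Suppose there is a true effect of 0.394 SD (borrowed from PROMIS satisfaction, 3.94/10) and the session-1 rating already absorbs part of it. Absorbing 0.1 or 0.2 SD lowers power from 84% to 60% or 31% at ρ = 0.2, from 96% to 80% or 45% at ρ = 0.5, and from about 100% to 99% or 83% at ρ = 0.8.

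**Precision if the session-1 rating is left out.** The variance factor for the T2-T4 mean alone is (1+2ρ)/3. It equals (4/3)(1−ρ) at ρ = 0.5, where both SEs are 0.105 SD. At ρ = 0.8 the SE rises from 0.067 SD (change) to √(0.867 × 2/120) = 0.120 SD. At ρ = 0.2 it falls from 0.133 to √(0.467 × 2/120) = 0.088 SD.

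**The case against.** The strongest reply is that much of the chain is inferred, and a good part of that reply stands.

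- A reader might infer that the treating therapist scores the targets. The text says the participant does; the therapist elicits the goals and conducts the session.
- A reader might infer that control involves no comparable step. The measure description has goals elicited in the first session of both conditions, and the arms are matched on number of sessions, telephone delivery, use of an occupational therapist and homework. Control session 1 is not itemised. What the documents support is a difference in surrounding content.
- Where in session 1 the ratings are made is not stated, and the ratings are not identified with the interview named in the BA/PS session description.
- The T1 mark belongs to a row shared with the PROMIS scales and productivity measures, so it may be a simplification of the table.
- Hypothesis 1b and the section 9 list of outcomes do not name the targets. Change from T1 reaches them only through the general rule, and no score is defined from the three ratings.
- A reader might infer a breach of intention to treat, because a woman who never has session 1 has no targets. The plan says "All available data from all participants who undergo randomization will be included in the analyses"; absent targets are missing data and do not contradict that sentence. They do mean that having targets depends on a post-randomisation event.

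These points narrow the concern without removing it. The two places still conflict, no pre-randomisation or blinded elicitation is described, and a secondary outcome falls under a rule that makes no exception for it.

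**Conclusion.** The concern holds in this limited form: the documents conflict on when and by whom the targets are first recorded. If the measure description is what was done, the general rule gives this outcome a baseline set after randomisation, in an unblinded session, that treatment may have moved.

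The size is unknown. The 16% and 48% rest wholly on the assumed SD, correlation and starting difference. The direction is unknown too, so the documents do not support reading those figures as inflated claims of benefit. If BA/PS session 1 raises starting satisfaction, the bias runs against BA/PS and the excess rejections favour control; if it lowers it, the bias favours BA/PS.

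Nor does this reach the main result. The PROMIS primary outcome, FACT-G and the other T1 measures are unaffected, and the targets enter no power calculation. It is worth correcting because the change is one of wording. Section 10 says that only data collection remains and that inferential analysis waits until it is complete.

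**What to change.** Reconcile the schedule with the measure description, and state when, by whom and in what setting the first ratings were taken. If that was session 1:

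1. Correct the T1 mark for this measure and label the session-1 ratings post-randomisation.
2. Exempt this outcome from the change-from-T1 contrast. Make the main comparison the T2-T4 ratings, adjusted for the stratification factors (site, time since treatment, chemotherapy), and say which of the three ratings is analysed.
3. Keep change from session 1 as a sensitivity analysis only.
4. Tabulate by arm the number attending session 1, the number of targets and the session-1 ratings.
5. State that the choice of targets, and who has any, remain post-randomisation, so the result is supportive only. Dropping the session-1 rating does not cure this: if the arms chose targets of different difficulty, the T2-T4 comparison inherits the difference.

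The cost is protocol and SAP wording, a weaker claim for one secondary outcome, and some loss of precision. Relative to the change contrast, that loss arises only if the within-subject correlation exceeds 0.5; relative to an analysis adjusted for a valid baseline, it arises at any positive correlation.

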Assessments. Assessments will be administered via telephone by a D-H research assistant blind to group assignment. Participants will complete outcome assessments upon enrollment (T1) and at 8 weeks (T2), 20 weeks (T3) and 44 weeks (T4) later. The T2 assessment captures the short-term outcomes of the most intensive part of the intervention (i.e., after six weekly sessions). The T3 assessment will capture the short-term outcomes at the end of the full intervention. The T4 assessment explores the sustained effect of BA/PS (six months after BA/PS ends). Our decision to include the T4 assessment was influenced by a systematic review that indicated it often takes six months to see maximum effects of interventions targeting participation in adults with physical disabilities.[46] The study aim is to test whether the BA/PS intervention affects the “slope” of functional recovery over time. With the longitudinal data, we will also be able to explore the pace of improvement and whether the two groups differ at these clinically relevant time points.

[figure not shown]
4. Subject Selection

Inclusion Criteria with justification

1. Age of 18 years or older.
2. Experiencing reduced participation (i.e., a score of ≥ 10 on the modified Work and Social Adjustment Scale[47]).
3. Females diagnosed with Stage 1-3 breast cancer and within one year of completion of locoregional treatment and/or chemotherapy with curative intent and absence of disease recurrence.

Biological variables of age and gender. In our pilot studies, the intervention has been flexible enough to be used with various challenges that occur across the age range.[25, 29] This proposal’s focus upon female breast cancer survivors reflects our pilot research population and allows us to focus recruitment resources with a smaller, closely aligned number of providers. We have decided to focus on females with breast cancer because of the very low prevalence rate of breast cancer in males. Because the D-H and UAB sites see a mean of 3.8 males each year with breast cancer, we will not enroll enough males to allow us to draw sound conclusions that are generalizable to a male population.

Medical co-morbidities. We considered the advantages and disadvantages of excluding women who have medical co-morbidities that affect their daily activities. Cancer survivors report an average of five

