Distress. *Hospital Anxiety and Depression Scale (HADS)* is a 14-item self-report measure of depressive and anxiety symptoms specifically designed for medical patients.[44] [45] The HADS contains only the cognitive symptoms of depression and anxiety, thus eliminating the somatic symptoms that are poor indicators of psychiatric distress in the medically ill. Items are rated on a four-point scale from 0 (not at all) to 3 (very often) and yield subscale scores for both depression and anxiety. Higher scores indicate more severe symptoms. Because breast cancer survivors can experience significant distress regarding their ability to perform social roles and life activities, we will use this scale to explore the potential efficacy of BA/PS on this outcome.

Perceived benefit. We have developed six questions modeled after those used in a recent rehabilitation RCT.[65] The questions will help us to describe the credibility and utility of the intervention versus control conditions. Using a three-point scale (not at all, some, a great deal), participants will rate the degree to which the program helped them gain confidence, reduce distress, adjust habits and routines, set goals, and exercise. These reflect the areas that participants in the pilot studies reported were affected by the intervention. It should also function as a manipulation check in that the intervention is hypothesized to work by setting goals and the control condition does not include goal setting as active component. At minimum, the intervention participants should report higher levels of benefit on the goal setting item.

Subject Stipends or Payments

Participants will be paid \$25 for completion of each of the Time 1, Time 2, and Time 3 assessments and will be paid \$30 upon completion of the Time 4 assessment (total = \$105 per participant). Participants who wish to accept the payments are required to complete a W9 form that will be submitted to Massachusetts General Brigham by the project coordinator along with the payment request. The W9 form will be completed on paper if the participant is recruited within clinic or will be completed via DocuSign software if recruited outside of the clinic (e.g., social media). DocuSign is HIPAA compliant and has been approved for use in this project by Dartmouth-Hitchcock.

Method for Assigning Subjects to Treatment Groups

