Scheme. Participants will be randomly assigned to group (1:1) using a computer-generated program overseen by [name]. The randomization scheme will be stratified by site (D-H and UAB), time since treatment completion (i.e., <6 months and >6 months), and receipt of chemotherapy (yes versus no) and will be blocked within strata (block lengths of 2 and 4 varied randomly).

Process and blinding. The PI or project managers will manage the randomization process, looking up the id number in an established excel file and assigning the local interventionist to communicate assignment to the participant and initiate treatment activities. The project coordinators will remain blind to group assignment and participants will be instructed not to discuss their assignment with the project coordinator collecting the outcome assessments.

When and How to Withdraw Subjects

Participants will be withdrawn from the study at their request (e.g., lack of interest in or perceived need for intervention, lack of time for study assessments).

Data Collection and Follow-up for Withdrawn Subjects

Our team continues to attempt to contact participants for each session and study assessment unless and until they ask us to stop/express the desire to withdraw. Each study contact is an extension of informed consent where participants are told what is occurring, what happens next, and that their participation is voluntary. When we are unable to reach participants by telephone for at least 30 days we send a letter conveying our attempts to reach them and ask them to contact us to continue with study activities or withdraw, as they prefer.

Treatment Regimen

Theoretical Background of BA/PS

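### The Perceived Benefit items, expected to differ by arm, sit in the blinded assessor's T2 telephone battery and may partly unblind that assessor before the T3 and T4 outcomes

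*Combined protocol and SAP*

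**What the plan says.** Section 3 (Assessments) states: "Assessments will be administered via telephone by a D-H research assistant blind to group assignment". Section 6 (Data Collection) repeats this: "A clinical research coordinator blind to group assignment will administer standardized telephone interviews, scheduled at the participants' convenience". A REDCap link or mailed form is offered only when a woman cannot or will not do the telephone interview.

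The one stated protection of the blind, apart from the declaration that coordinators stay blind, is in Section 6 (Process and blinding): "participants will be instructed not to discuss their assignment with the project coordinator collecting the outcome assessments".

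In the Section 6 schedule, the row "Perceived Benefit Questions" has a single mark, at T2 (week 8). The Perceived benefit paragraph describes a three-point rating of how far the program helped the woman gain confidence, reduce distress, adjust habits and routines, set goals, and exercise. It gives the items a second purpose: "It should also function as a manipulation check in that the intervention is hypothesized to work by setting goals". It adds: "At minimum, the intervention participants should report higher levels of benefit on the goal setting item".

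The primary outcome, PROMIS Satisfaction, is collected at T1 to T4. Section 9 (Modeling) defines the overall treatment effect as the between-group difference in change from T1, averaged over T2 to T4.

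**The concern.** Women are told not to reveal their arm to the assessor. The schedule then places in the assessor's own T2 interview an item included partly because its answers should separate the arms. The better it works as a manipulation check, the more it tells the person who may later collect T3 and T4.

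The text available for review gives these items to no other person or mode, fixes no position for them within the T2 call, and does not hide the answers from later callers. T2 also enters the averaged effect. If the items precede PROMIS at T2, all three post-baseline terms are exposed; if they follow it, two of the three are.

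At stake is interviewer-related bias in an outcome that staff read out and enter, and how firmly the report can claim blinded assessment.

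**Working it through.** **1. Placement.** The telephone battery is assigned to the blinded assessor without exception (Sections 3 and 6), and the schedule marks these items at T2. That the assessor asks them is therefore an inference, but nothing available contradicts it. The row was read from an extracted table; its single mark falls under T2.

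**2. The plan's sample size reproduces, so its inputs can be reused.** Section 9 gives SD 10, MID 3.94, alpha .017, 80% power, three post-baseline visits and correlation ρ from 0.2 to 0.8. Taking the test as two-sided:

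n per arm = 2(2.387 + 0.842)² × 10² × [(1 + 2ρ)/3] / 3.94²

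This gives 62.7 at ρ = 0.2 and 116.4 at ρ = 0.8, which round up to the stated 63 and 117. With 240 completers there are 120 per arm.

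**3. How much one answer reveals.** The documents give no response rates, so these are assumptions. Let p₁ and p₀ be the shares answering *a great deal* in BA/PS and control. With 1:1 allocation, guessing BA/PS for that answer is right with probability 0.5 + (p₁ − p₀)/2. For 70% vs 25% this is 0.5 + 0.45/2 = 72.5%.

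**4. From guess to bias.** Let b be the assumed shift in recorded score between women *guessed* to be in BA/PS and those guessed to be in control, at T3 and T4 only. The net shift between true arms is (p₁ − p₀)b. T3 and T4 are two of three terms, so:

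bias in the T2–T4 average = (2/3)(p₁ − p₀)b

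With 70% vs 25% and b = 1: (2/3)(0.45) = 0.30 points, and 0.30/3.94 = 8% of the MID.

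**5. False-positive rate.** A nominal two-sided 5% test is used as a yardstick, with two standard errors:

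- Post-baseline average, as in the sample-size calculation: 10√{[(1 + 2ρ)/3] × 2/120} = 0.88 (ρ = 0.2) to 1.20 (ρ = 0.8).
- Raw change from T1, as in the Section 9 contrast: 10√{[4(1 − ρ)/3] × 2/120} = 1.33 (ρ = 0.2) to 0.67 (ρ = 0.8).

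Rate = 1 − Φ(1.96 − bias/SE) + Φ(−1.96 − bias/SE). For b = 1:

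| *A great deal*, BA/PS vs control | Guess right | Bias (points) | Share of MID | Rate, post-baseline SE (ρ 0.2 / 0.8) | Rate, change SE (ρ 0.2 / 0.8) |
|---|---|---|---|---|---|
| 60% vs 40% | 60% | 0.13 | 3% | 5.3% / 5.1% | 5.1% / 5.5% |
| 70% vs 25% | 72.5% | 0.30 | 8% | 6.3% / 5.7% | 5.6% / 7.4% |
| 80% vs 15% | 82.5% | 0.43 | 11% | 7.8% / 6.5% | 6.2% / 10.0% |
| Arm fully known | 100% | 0.67 | 17% | 11.8% / 8.6% | 7.9% / 17.0% |

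Bias is proportional to b, so b = 2 doubles it. If the items precede PROMIS at T2 and the shift acts there too, the factor 2/3 becomes 1: for 70% vs 25% and b = 1, the bias is 0.45 points (0.45/3.94 = 11% of the MID).

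**6. What can still change.** The protocol is dated January 2023. Section 10 (Internal Data and Safety Monitoring Board) says enrollment and intervention are complete and only data collection remains. The intervention lasts about four months. T2 is at week 8, with calls ending four weeks later, at week 12. Every woman is therefore past T2.

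**The case against.** A reader might infer that the T2 call tells the assessor the allocation, and that assessor blinding is void from then on. The documents do not support that. They predict a difference between groups on a three-point item, not a distinct answer from each woman, and the question refers neutrally to the program. The Individual Activity Targets paragraph has recovery goals elicited at session 1 in both arms. The control covers physical activity, stress management and work accommodations, with homework, so a control woman may well endorse several items. The 0.67-point bias needs every allocation to be known. This objection stands, and the size given here is reduced accordingly.

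The route to bias is also narrow. The outcome is self-reported on fixed responses, interviews are standardized, women have a response choice sheet, and call attempts follow a fixed window. That limits b but does not make it zero, because staff still conduct the interview and enter the answers.

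Nor do the documents say that the same person calls a woman at T2, T3 and T4. Section 3 moves data collection to MGH IHP once enrollment has been completed in 2022, which may already change some callers. Whether staff changed is not stated, nor whether the new caller can see the T2 answers.

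Finally, the planned inference is a multiple-degree-of-freedom interaction test with FDR at 10%. The nominal 5% rates above are therefore a yardstick, not the trial's actual error rate.

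**Conclusion.** The point holds as a risk of partial unblinding. Items expected to differ by arm are scheduled in the blinded assessor's T2 battery, with no stated separate administrator, order or masking. The assessor can guess better than chance before T3 and T4, and before PROMIS at T2 if the items come first.

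The size cannot be known from the documents. At 70% vs 25% and a 1-point shift between guessed arms at T3 and T4, the bias is about 0.30 points (8% of the MID), and the nominal 5% false-positive rate becomes about 6–7% (5.6% to 7.4% across both standard errors and ρ from 0.2 to 0.8). Both the response rates and the shift are assumptions. So is the premise that whoever calls at T3 and T4 made the T2 call or can see its answers. The effect is modest under these assumptions, but it was cheap to avoid and should be acknowledged when assessor blinding is claimed.

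**What to change.** **In the plan, and for any successor trial:** take the Perceived Benefit items out of the assessor's T2 call. Collect them by the self-completed REDCap survey or mailed form that Section 6 already provides, with answers not visible to the assessor. Alternatively, ask them last at T4, after all outcomes are recorded. State the choice in the schedule.

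**In this trial, where every woman is past T2:**

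- Hide the T2 Perceived Benefit record from whoever makes the remaining calls.
- Where possible, have those calls made by existing staff who did not make that woman's T2 call. Masking the record does not remove what a T2 caller remembers.
- Optionally, record the assessor's guess of allocation at the end of the last call.
- In the report, say who asked these items and where they came in the T2 interview, and qualify the assessor-blinding claim.

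**Cost:** one schedule line, one form permission and some call assignment within existing staff. Self-completion may leave slightly more missing answers on a descriptive form; moving the items to T4 lengthens recall. The sample size is unaffected.
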